Study Period (SP)	SP I- Screening	SP II- Prospective Baseline	SP III – Treatment										SP IV – Follow-up	
			30- 45	14	16	30	30	30	15	15	15	15	60	60
(Target) Interval (days) since previous visit														
Allowable range (days) between visits	3-45	30-40 ^a												
Interval allowance (days) compared from previous visit				± 1	± 3	± 2	± 2	± 2	± 2	± 2	± 2	± 2	± 5	± 5
Visit	1	2	3	4 ^b	5	6	7	8	9 ^c	10	11 ^c	12/ET	13	14/ET
Month			0	0.5	1	2	3	4	4.5	5	5.5	6	8	10
Informed consent	X													
Inclusion/exclusion	X	X	X											
Demographics	X													
Physical examination ^d	X													
Height	X													
Weight	X											X		X
Waist and hip circumference	X													
Medical history	X													
Pre-specified migraine history		X												
Substance use	X													
Prior Therapy (Migraine Medication)	X													
ECG ^e	X		X									X		X
Vital signs ^f	X		X		X	X	X	X		X		X	X	X
Adverse events	X	X	X	X	X	X	X	X	X	X	X	X	X	X
Concomitant medications	X	X	X	X	X	X	X	X	X	X	X	X	X	X
ePRO training		X												
ePRO daily patient entries ^g		X	X	X	X	X	X	X	X	X	X	X	X	X
Patient training video			X											
Hematology	X		X				X					X		X
Clinical chemistry	X		X				X					X		X

Study Period (SP)	SP I- Screening	SP II- Prospective Baseline	SP III – Treatment										SP IV – Follow-up	
			30-45	14	16	30	30	30	15	15	15	15	60	60
(Target) Interval (days) since previous visit			30-45	14	16	30	30	30	15	15	15	15	60	60
Allowable range (days) between visits	3-45	30-40 ^a												
Interval allowance (days) compared from previous visit				± 1	± 3	± 2	± 2	± 2	± 2	± 2	± 2	± 2	± 5	± 5
Visit	1	2	3	4 ^b	5	6	7	8	9 ^c	10	11 ^c	12/ET	13	14/ET
Month			0	0.5	1	2	3	4	4.5	5	5.5	6	8	10
HbA1c			X									X		X
Urinalysis ^h	X		X									X		X
Serum Pregnancy (for women of childbearing potential) ⁱ or FSH at Visit 1 (for women who have evidence of cessation of menses for at least 12 months)	X											X		X
Urine pregnancy ^j			X		X	X	X	X		X		X ^m		
Urine drug screen	X													
Immunogenicity ^j			X	X	X	X	X					X		X
Biomarker storage sample ^j			X		X		X			X		X ^m		X
CCI [REDACTED]		X	X	X	X	X	X	X	X	X	X	X	X	X
PK blood sample ^j				X	X	X	X	X	X	X	X	X	X	X
CCI [REDACTED]			X											
Whole blood RNA/epigenetic sample ^j			X									X		X
Study drug administered ^k			X		X	X	X	X		X				
MIDAS			X				X					X		X
MSQ v2.1			X		X	X	X	X		X		X		X
PGI-S			X		X	X	X	X		X		X		X
PGI-I					X	X	X	X		X		X		X

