Study Period (SP)	SP I- Screening	SP II- Prospective Baseline	SP III – Treatment										SP IV – Follow-up	
			30-45	14	16	30	30	30	15	15	15	15	60	60
(Target) Interval (days) since previous visit														
Allowable range (days) between visits	3-45	30-40 ^a												
Interval allowance (days) compared from previous visit				± 1	± 3	± 2	± 2	± 2	± 2	± 2	± 2	± 2	± 5	± 5
Visit	1	2	3	4 ^b	5	6	7	8	9 ^c	10	11 ^c	12/ET	13	14/ET
Month			0	0.5	1	2	3	4	4.5	5	5.5	6	8	10
PSMQ-M					X							X		
HCRU and Employment status			X		X	X	X	X		X		X	X	X
C-SSRS/SHSF, SHFU ^f	X	X	X		X	X	X	X		X		X	X	X

Abbreviations: AE = adverse event; CGRP = Calcitonin-gene related peptide; CRP = Lilly Clinical Research Physician; CRS = Lilly Clinical Research Scientist; C-SSRS = Columbia Suicide Severity Rating Scale; DNA = deoxyribonucleic acid; ECG = electrocardiogram; ePRO = electronic patient-reported outcomes; ET = early termination; FSH = follicle stimulating hormone; HbA1c = glycated hemoglobin; HCRU = Health Care Resource Utilization; MIDAS = Migraine Disability Assessment test; MSQ (v2.1) = Migraine Specific Quality of Life Questionnaire; PGI-I = Patient Global Impression of Improvement; PGI-S = Patient Global Impression of Severity; PK = pharmacokinetics; PSMQ-M = Patient Satisfaction with Medication Questionnaire-Modified; RNA = ribonucleic acid; SP = Study Period; SHSF = Self-harm supplement form; SHFU = Self-harm follow-up form.

Note: Selected tests may be obtained in the event of a treatment-emergent hepatic abnormality, and follow-up may be required with patients, in consultation with the Lilly, or its designee (CRP/CRS). See [Appendix 4](#) for more details regarding specific hepatic monitoring tests. If the patient has discontinued the trial and returns for hepatic follow-up, the site should use the 800 series as the visit designation.

- ^a The eligibility period of the prospective baseline assessment will last from 30 to 40 days. Investigators and patients may have up to an additional 5 days to schedule their Visit 3 appointment (beyond the 40 days); however, eligibility will be based on the 30-40 day period.
- ^b Visit is to include a review of any spontaneously reported AE, concomitant medications and collection of blood samples for immunogenicity, PK, and CGRP plasma.
- ^c Visit is to include a review of any spontaneously reported AE, concomitant medications and collection of blood samples for PK, and CGRP plasma.

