9.9. Medical Resource Utilization and Health Economics

Health economic, disability, and quality of life assessments of galcanezumab in patients with migraine, except for healthcare resource utilization (HCRU) will be collected through the use of an eCOA system, as described in the Data Capture System section of [Appendix 3](#). The assessments will be based on the following scales:

Migraine Disability Assessment test (MIDAS): The MIDAS was designed to quantify headache-related disability over a 3-month period. This instrument consists of 5 items that reflect the number of days reported as missing, or with reduced productivity at work or home and social events; a higher value is indicative of more disability (Stewart et al. 1999; Stewart et al. 2001). This instrument is considered highly reliable and valid; and is correlated with clinical judgment regarding the need for medical care (Stewart et al. 1999; Stewart et al. 2001).

Migraine Specific Quality of Life questionnaire version 2.1 (MSQ v2.1): The MSQ v2.1 is a self-administered health status instrument, and was developed to address physical and emotional limitations of specific concern to individuals suffering from migraine headaches. The instrument consists of 14 items that address 3 domains: (1) Role Function-Restrictive; (2) Role Function-

Preventive; and, (3) Emotional Function (Jhingran et al. 1998). The instrument was designed with a 4- week recall period, and is considered reliable, valid and sensitive to change in migraine (Jhingran et al. 1998; Rendas-Baum et al. 2013). Clinically meaningful differences for each domain have been established and are widely used in the literature.

Health Care Resource Utilization (HCRU) and Employment Status: The HCRU will be solicited by study personnel while documenting patient responses. The HCRU consists of 3 questions, asking about hospital emergency room visits, overnight stays in a hospital, and any other visits with a healthcare professional that occurred since their last study visit. Patients are also specifically asked about the number of healthcare events that are related to migraine headaches, outside of visits associated with their participation in the clinical trial. The baseline visit will include the same questions, however, with the frame of reference being over the last 6 months. A question on employment status is also solicited, given the correlation and potential confounding with health outcomes measures.

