#### 5.4.3.3. HCRU (HealthCare Resource Utilization and Employment Status) Questionnaire and employment status

The Healthcare Resource Utilization (HCRU) will be solicited by study personnel while documenting patient responses. The HCRU consists of 3 questions;

1. Hospital emergency room visits since your last study visit (YES/NO)
  - a. If yes, how many times did you go to a hospital emergency room?
  - b. How many of these times going to a hospital emergency room were related to your migraine headaches?
2. Overnight stays as a patient in a hospital since your last study visit (YES/NO)
  - a. If yes, how many different times were you as a patient in a hospital overnight?

- How many days total were you in the hospital for overnight stay?
  - b. How many of these times, as a patient in a hospital overnight, were related to your migraine headaches?
  - c. How many days total, as a patient in a hospital overnight, were related to your migraine headaches?
3. Any other visits with a healthcare professional that occurred since your last study visit (YES/NO)
- a. If yes, how many different times did you visit a healthcare professional?
  - b. How many of these times, visiting a healthcare professional, were related to your migraine headaches?

Regarding question 3, patients are specifically asked about the number of healthcare events that are related to migraine headaches, outside of visits associated with their participation in the clinical trial.

The baseline visit will include the same questions, however, with the frame of reference being over the last 6 months.

A question on employment status is also solicited, given the correlation and potential confounding with health outcomes measures. More specifically, one of the following statuses with additional information will be recorded.

- Working for pay
  - average number of hours worked (hours/week)
  - how long has the patient had this job? (number of weeks)
- Student
- Keeping house (full-time)
- Volunteer work
  - average number of hours volunteered (hours/week)
- Unemployed, *not* due to study disease disability
- Unemployed, due to study disease disability
- Retired
- Self-employed

There will be no imputation for missing values.

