### 5.5.11.3. HCRU

For HCRU, descriptive summary of Question 1-3 will be created. Analysis period is SP I/II/III/IV combined. It includes baseline (over the last 6 months period from Visit 3), SP III (6 months period), and SP IV (4 months period) with ITT population. In particular, for each period, the summary of following will be created:

- number of emergency room visits (Q1)
- number of emergency room visits related to migraine (Q1)
- number of overnight hospitalization (unit=incidence) (Q2)
- number of overnight hospitalization related to migraine (unit=incidence) (Q2)
- number of overnight hospitalization (unit=day) (Q2)
- number of overnight hospitalization related to migraine(unit=day) (Q2)
- number of healthcare professional visits (Q3)
- number of healthcare professional visits related to migraine (Q3)

Summary of HCRU related to migraine will be created. The unit is per 100 patient years. 100 patient year is defined as

$$100 * (\text{sum of all events}) / (\text{number of total months with patient data} / 12).$$

Descriptive summary of working status (Question 4) will be created for each month: Analysis period is SP III/IV combined. It includes month 0 to month 6, month 8, and month 10 with ITT population.

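### HCRU asks about events since the last study visit but is not collected at Visits 4, 9 and 11, so as worded 44 of 180 treatment-phase days fall outside every recall window

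*SAP*

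**What the plan says.** SAP 5.4.3.3 lists three HCRU items: emergency room visits, overnight hospital stays and other healthcare visits. Each has the same look-back. The first reads "Hospital emergency room visits since your last study visit (YES/NO". Protocol 9.9 words it the same way for the third item: "any other visits with a healthcare professional that occurred since their last study visit". Baseline differs: "The baseline visit will include the same questions, however, with the frame of reference being over the last 6 months".

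The Schedule of Activities (protocol Section 2) marks HCRU nine times: at Visits 3, 5, 6, 7, 8, 10, 12, 13 and 14. The cells for Visits 4, 9 and 11 are blank. These three are nonetheless study visits with procedures of their own. The footnote for Visits 9 and 11 says "Visit is to include a review of any spontaneously reported AE, concomitant medications and collection of blood samples for PK, and CGRP plasma". The Visit 4 footnote is similar, with "collection of blood samples for immunogenicity, PK, and CGRP plasma".

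SAP 5.5.11.3 summarises HCRU by period: "It includes baseline (over the last 6 months period from Visit 3), SP III (6 months period), and SP IV (4 months period"). For migraine-related events it adds a rate per 100 patient-years, which divides events by the total months with patient data over 12. SAP Table CGAN. 4.2 also describes the HCRU endpoint as a descriptive summary at each visit.

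**The concern.** A question that looks back to the last study visit covers all the time between interviews only if it is asked at every study visit. Here it is not. At Visit 10 the previous study visit is Visit 9, where HCRU was not asked, so the time between Visits 8 and 9 belongs to no interview. The same happens before Visits 4 and 11.

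Neither document redefines the look-back as running from the last HCRU interview, and neither removes the uncovered days from the period length or the rate denominator. All the scheduled gaps lie in Study Period III. Baseline asks about a full six months, and no scheduled visit is skipped in Study Period IV. Events would therefore be undercounted in one of three periods that are summarised together. The look-back also varies in length from visit to visit, which matters for any by-visit display.

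**Working it through.** **Inputs.** Target days since the previous visit, for Visits 4 to 14, from protocol Section 2: "14 16 30 30 30 15 15 15 15 60 60". Allowances are ±1 day at Visit 4, ±3 at Visit 5 and ±2 at each of Visits 6 to 12. HCRU visits are as listed above.

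**The plan's own period lengths.**
- SP III: 14 + 16 + 30 + 30 + 30 + 15 + 15 + 15 + 15 = 180 days; 180/30 = 6 months.
- SP IV: 60 + 60 = 120 days; 120/30 = 4 months.

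Both agree with SAP 5.5.11.3.

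**Coverage under the literal wording.**

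| HCRU at | Looks back to | Days covered | Days since previous HCRU | Days missed |
|---|---|---|---|---|
| Visit 5 | Visit 4 | 16 | 30 | 14 |
| Visit 6 | Visit 5 | 30 | 30 | 0 |
| Visit 7 | Visit 6 | 30 | 30 | 0 |
| Visit 8 | Visit 7 | 30 | 30 | 0 |
| Visit 10 | Visit 9 | 15 | 30 | 15 |
| Visit 12 | Visit 11 | 15 | 30 | 15 |
| SP III total | | 136 | 180 | 44 |
| Visit 13 | Visit 12 | 60 | 60 | 0 |
| Visit 14 | Visit 13 | 60 | 60 | 0 |

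The gap is 44/180 = 24.4% of SP III, and 136/180 = 75.6% is covered.

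**Range within the visit windows.**
- The missed intervals total 13 + 13 + 13 = 39 days at the shortest and 15 + 17 + 17 = 49 at the longest.
- The other six intervals total 136 ± (3 + 2 + 2 + 2 + 2 + 2) = 136 ± 13 days.
- The extreme fractions are 39/(39 + 149) = 20.7% and 49/(49 + 123) = 28.5%.

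**Effect on the rate.** Assume literal administration, a constant true rate, and a denominator equal to full SP III time. Expected recorded events are then proportional to 136 days and the denominator to 180, so reported rate = true rate × 136/180 = 0.756 × true rate. With an assumed 100 events per 100 patient-years, the table would show 75.6. The proportional shortfall is the same whatever the true rate.

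**Effect on arm comparisons.** Let the constant true rates be a and b in two arms with the same coverage.
- Difference: 0.756a − 0.756b = 0.756(a − b), so absolute differences shrink by 24.4%.
- Ratio: 0.756a/0.756b = a/b, which is unchanged.

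**Effect on a by-visit display.** At a constant rate, relative to Visits 6 to 8, the expected count is 16/30 = 53% at Visit 5 and 15/30 = 50% at Visits 10 and 12.

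**After the correction.** If each interview looks back to the previous HCRU interview, 180 of 180 days are covered.

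**The case against.** The strongest objection is that literal administration is not established. Study personnel put the questions and record the answers, and the documents include neither the form's instructions nor site guidance. An interviewer may well have asked about the time since the last HCRU interview, in which case there is no gap. This stands: the documents show what the wording covers, not what was asked. But nothing in them tells sites to depart from the wording.

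A reader might infer that the table will show healthcare use falling on treatment and rising again afterwards. The documents do not support that as a prediction.
- The fall needs a constant event rate and complete six-month recall at baseline. Under-recall at baseline would offset it by an amount the documents do not give.
- Taken alone, the gap would make the SP IV rate 180/136 = 1.32 times the SP III rate. But about 240 of some 451 patients are expected to roll over to CGAP and skip SP IV (protocol 5.1 and 7.8.1), and those who remain may start preventive medication from one month after Visit 12. The recall gap is only one of several influences on that comparison.

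The weight of the endpoint is also limited. HCRU is an other-secondary measure, and the SAP revision history records its change from statistical models to simple descriptive statistics. The visit schedule is the same in every arm, so no bias is expected in between-arm ratios. If the treatment effect varies over time, the ratio would describe the covered days only.

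The denominator is not fully defined either. Months with patient data most naturally means full time in the period, but the SAP does not say so. Finally, inpatient hospitalisation is a serious adverse event criterion and adverse events are reviewed at every visit, so some overnight stays could be recovered from safety data. Emergency room visits without admission and ordinary healthcare visits have no such dependable backup.

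**Conclusion.** The wording and the schedule do not fit together. As written, 44 of 180 target SP III days (24.4%; about 21% to 28% within the visit windows) lie outside every HCRU recall window, and the remaining windows vary between 15, 16 and 30 days. That much follows from the documents alone.

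The effect on results is conditional. With literal administration and a constant true rate, SP III counts would be about 76% of the true count. The migraine-related rate would be understated equally if its denominator is full SP III time. Absolute rates, absolute arm differences, comparisons of SP III with baseline or SP IV, and by-visit summaries could then mislead. Between-arm rate ratios are not expected to be biased, and the primary and key secondary analyses are untouched. The point merits correction because the remedy is simple, not because it threatens the trial's conclusions.

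**What to change.** Reword the look-back in protocol 9.9, on the HCRU form and in SAP 5.4.3.3, so that it runs from the last time these questions were asked. The interviewer should read that date out: Visit 3 when asking at Visit 5, Visit 8 at Visit 10, and Visit 10 at Visit 12.

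For data already collected, first confirm with sites how the questions were put.
- If sites asked about the time since the last HCRU interview, state this in the study report and leave the analysis as it is.
- If they followed the wording, define the SAP 5.5.11.3 denominator as the person-time covered by the recall windows, using actual visit dates, and state that SP III counts are not six-month totals. Any by-visit summary should show the length of each window or be expressed per covered day.

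In either case the SAP should say exactly what months with patient data means. The cost is a one-line wording change with a site memo, or a redefined denominator and a note in descriptive tables. No visit or procedure is added.

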#### **5.4.3.4. PSMQ-M (Patient Satisfaction with Medication Questionnaire-Modified) Questionnaire**

The Patient Satisfaction with Medication Questionnaire-Modified (PSMQ-M) is a self-rated scale which measures patients' levels of satisfaction with study medication (Kalali 1999). The scale has been modified for use in this study, assessing 3 items related to the clinical trial treatment over the past 4 weeks: satisfaction, preference, and side effects.

Satisfaction responses range from "very unsatisfied" to "very satisfied" with the current treatment (5 categories).

Preference compares the current study medication to previous medications, with responses from "much rather prefer my previous medication" to "much rather prefer the medication administered to me during the study" (5 categories).

The side effects responses range from "significantly less side-effects" to "significantly more side-effects" (5 categories).

Positive response for each item are defined as follows:

- Satisfaction : "Very satisfied" or "Somewhat Satisfied"
- Preference : "Much Prefer Study Medication" or "Prefer Study Medication"
- Side Effects: "Much Less Side Effects" or "Less Side Effects"

The PSMQ-M will be collected at Month 1 and Month 6.

#### **5.4.4. Safety Endpoints**

Safety endpoints consist of the incidences of treatment emergent adverse events (TEAEs), serious adverse events (SAEs) and adverse events (AEs) leading to discontinuation, follow-up-emergent adverse events (FEAEs) during Study Period IV, vital signs (blood pressure, pulse, and body temperature), weight, suicidal ideation and behaviors assessed by solicited questioning using the Columbia-Suicide Severity Rating Scale (C-SSRS), electrocardiograms (ECGs), and laboratory measures (chemistry, hematology, and urinalysis).

#### **5.4.5. Immunogenicity Endpoints**

Immunogenicity endpoints consist of the incidences of anti-drug antibodies (ADAs) in all trial participants at baseline (pre-existing ADAs), and in all trial participants at post-baseline (treatment emergent ADAs). An additional endpoint is the incidence of neutralizing antibodies (NABs) present in those trial participants with ADAs.

CCI

#### **5.4.7. Pharmacokinetic Assessment**

Serum LY2951742 concentration will be determined in trial participants following LY2951742 administration at specified visits throughout the trial. Pharmacokinetic assessments will be summarized in the PK/PD analysis plan described in the protocol.

### **5.5. Statistical Analyses**

The SAP Version 1 was approved prior to first patient visit and SAP Version 2 prior to any unblinding of the study team. The SAP supersedes the statistical plans described in the protocol.

#### **5.5.1. General Considerations**

Unless otherwise specified, analyses will be conducted on an intent-to-treat (ITT) population, which will include all patients who are randomized at Visit 3 and receive at least 1 dose of study drug. Patients in the ITT population will be analyzed according to the treatment group to which they are randomized. When change from baseline is assessed, the patient will be included in the analysis only if he/she has a baseline and a post-baseline measurement.

Unless otherwise specified, hypothesis tests will be based on two-sided alpha level of 0.05. Ninety-five percent confidence intervals (CIs) for the difference in least-square means (LSMeans) between treatment groups (LY2951742 and Placebo) will be provided.

For the primary analysis (overall mean change from baseline during the 6-month double blind period), multiplicity adjustment (120 mg versus placebo and 240 mg versus placebo), step-down Dunnett procedure, will be used.

Change from baseline of continuous variables with repeated measures will be analyzed using a mixed model repeated measures (MMRM) analysis. An MMRM analysis refers to a restricted maximum likelihood (REML)-based, mixed-effects repeated measures analysis using all the longitudinal observations at each post-baseline visit.

In addition to the MMRM approach, sensitivity analysis of covariance (ANCOVA) model using the last observation carried forward (LOCF) to account for missing data will be conducted to provide additional information for the primary analysis.

For other continuous variables without repeated measures, the change from baseline to LOCF endpoint will be analyzed using an analysis of variance (ANOVA) or ANCOVA model.

Unless otherwise specified, when an ANOVA model or ANCOVA model is used to analyze a continuous efficacy variable, type III sum-of-squares for the least-squares means (LSMean) will be used for the statistical comparisons.

Visit-wise binary efficacy variables will be analyzed using a generalized linear mixed model (GLIMMIX) as pseudo-likelihood-based mixed effects repeated measures analysis for categorical data (MMRM-CAT).

For categorical efficacy variables without repeated measures, comparisons between treatment groups will be performed using logistic regressions (see Section 5.5.1.1 for details).

For other categorical variables without repeated measures, comparisons between treatment groups will be performed using Fisher's exact tests unless otherwise specified. For example,

- Baseline patient characteristics
- Safety measures (including percentages of patients with TEAEs, SAEs, and AEs reported as a reason for discontinuation, as well as those patients who met categorical criteria for changes in vital signs and weight, ECGs, and laboratory tests)

Only scheduled visit data will be available for the following data. In other words, there will be no unscheduled visit data;

- Patient migraine headache data collected by ePRO diary
- PGI-S
- PGI-I
- MSQ v2.1
- MIDAS
- PSMQ-M
- HCRU

For details of analysis methods, please refer to the following sub-sections.

Any change to the data analysis methods described in the protocol will require an amendment ONLY if it changes a principal feature of the protocol. Any other change to the data analysis methods described in the protocol, and the justification for making the changes, will be described in the statistical analysis plan and/or in the clinical study report.

Additional exploratory analyses of the data will be conducted as deemed appropriate.

Statistical analysis of this study will be the responsibility of Eli Lilly and Company or designee. SAS® software will be used to perform most or all statistical analyses.

Post-Treatment Emergent and Follow-up Emergent are used interchangeably in this study.

Efficacy analysis baseline related values are based on eligibility day derived from ePRO data, not IWRS data (see Section 5.4.1 for the eligible day definition).

Summary tables will display each arm (placebo, LY120, LY240). In addition, if the summary is sorted by LY\_All arm (LY120 and LY240 combined), then LY\_All will also be shown (e.g. summary of TEAE). For some baseline characteristic values (e.g. previous prevention therapy), frequencies will be sorted by “total” (placebo, LY120, and LY240 combined) and “total” will be also displayed.

The measurements of PGI-I, PGI-S, MSQ, MIDAS PSMQ-M, or HCRU will be used if they are taken on the same day of the injection date even if the measurements are after injection timing. But if it is after the injection day, then it will be excluded.

Unless otherwise specified, SPIII and SPIV combined analysis will be performed only for the primary and the key secondary analysis. That is,

- Mean change from baseline in the number of MHD
- The proportion of patients with reduction from baseline  $\geq 50\%$
- The proportion of patients with reduction from baseline  $\geq 75\%$
- The proportion of patients with reduction from baseline =100%
- Mean change from baseline in the Role Function-Restrictive domain score of MSQ
- Mean change from baseline in the number of MHD requiring medication for the acute treatment of migraine
- Mean change from baseline in PGI-S

For PGI-I, PGI-S, and MSQ analysis with repeated measurement in SP III (both continuous and binary outcomes), both average of month 4 to month 6 and overall (month 1 to month 6) will be shown for treatment comparisons.

